Hypothesis	The primary hypothesis of this study is that using HeartFlow's FFR _{CT} analysis as part of the treatment pathway for clinically stable, symptomatic patients with suspected CAD in the ED/observation unit can result in a more streamlined diagnostic pathway and therefore provide cost-effective clinical care for patients.
Population	The population for this study will be clinically stable, symptomatic patients who present to the ED or observation unit with suspected CAD and no history of coronary artery disease, and who while in the ED or observation unit have a CCTA performed which shows at least one $\geq 40\%$ lesion and no lesions $> 90\%$ in a major epicardial vessel, and a successfully processed FFR _{CT} (if applicable).

Study Design and Methods	
This is a prospective multi-center study. All clinically stable, symptomatic patients who present to the ED or observation unit with suspected CAD and who have at least one $\geq 40\%$ lesion and no lesions $< 90\%$ lesion in a major vessel, confirmed by CCTA, are eligible for enrollment once their CCTA has been completed and FFR_{CT} (if applicable) has been ordered. All enrolling sites will have CCTA incorporated into their standard evaluation of chest pain in the ED/observation unit. Non-control sites will have CCTA and FFR_{CT} analysis incorporated into their standard evaluation of chest pain in the ED/observation unit.
 
All sites will provide demographics, medical history, CCTA images, FFR_{CT} (for non-control sites), the decision plan post CCTA and pre FFR_{CT} (for non-control sites), length of stay for patients in the ED/observation unit/hospital, billing reports (UB-04 preferred), 30-day clinical outcomes, and any other hospital or office visits, imaging, and/or procedural data completed prior to the follow-up 30-day visit.
 
Sites which do not have FFR_{CT} incorporated into the ED/observation unit will be control sites. If FFR_{CT} is implemented at a control site during the enrollment period, the site can request to switch over to the non-control arm once FFR_{CT} has been successfully implemented in the ED/observation unit at that site. This switch must be reviewed and approved by the HeartFlow Clinical Research team.

Primary Endpoint	The primary endpoint of ADVANCE-ED is the reclassification rate between the coronary management plan based on the review of the CCTA compared to the actual management.

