Secondary Endpoints	
The secondary endpoints include:
 
 • Cost utility analysis to include length of stay in ED/observation unit and overall, secondary CAD testing, and invasive procedures • Major Adverse Coronary Event (MACE) rates at day 30 • Rate of invasive catheterization without obstructive disease at day 30 • Time to diagnosis • Time to discharge

Inclusion Criteria	
Inclusion criteria (all must be present):
 
 1. Age ≥ 18 years 2. Clinically stable, symptomatic patients who present to ED/observation unit with suspected CAD 3. CCTA shows at least one $\geq 40\%$ lesion and no lesions $>90\%$ in at least one major epicardial vessel 4. FFR_{CT} processed successfully (if applicable) 5. EKG with no acute ischemic changes 6. Willing to comply with all aspects of the protocol, including adherence to follow up visit 7. Agrees to be included in the study 8. Able to provide written informed consent
Exclusion Criteria	
Exclusion criteria (all must be absent):
 
 1. CCTA showing no $\geq 40\%$ lesion in a major epicardial vessel 2. CCTA showing a lesion $>90\%$ in a major epicardial vessel 3. CCTA showing other incidental, non-cardiac findings requiring admission, e.g., pneumonia, pulmonary embolism, or aortic dissection 4. Uninterpretable CCTA which is not of diagnostic quality 5. CABG or PCI prior to CCTA acquisition 6. Left main lesion $>50\%$ 7. Confirmed acute coronary syndrome (acute myocardial infarction or unstable angina) 8. Known complex congenital heart disease or any history of coronary artery disease 9. Patients with tachycardia or significant arrhythmia which cannot be adequately controlled with medications to allow CTA 10. Any active, serious, life-threatening disease with a life expectancy of less than 2 months 11. Inability to comply with follow-up requirements 12. Currently enrolled in another study utilizing FFR_{CT} or in an investigational trial that involves a non-approved cardiac drug or device 13. Persons under the protection of justice, guardianship, or curatorship
Study Follow-Up	There will be a 30-day follow-up phone visit following the baseline visit.
Clinical Research Organization	
Peachtree BioResearch Solutions [name]

Sponsor	HeartFlow, Inc. [name]
---------	--

I. BACKGROUND AND RATIONALE

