- Cost utility analysis to include length of stay, secondary coronary testing, and invasive coronary procedures
- Major Adverse Coronary Event (MACE) rates at day 30
- Rate of invasive catheterization without obstructive disease at day 30
- Time to diagnosis
- Time to discharge

IV. STUDY DESIGN

All non-invasive and invasive data collected will be obtained from clinical practices that are standard clinical care. All details about cardiovascular testing and treatment (planned and actual) will be recorded at baseline.

IV. A. Location and Number of Subjects

Approximately 500 subjects will be enrolled from approximately 20 experienced clinical research sites across the US.

All enrolling sites will have CCTA incorporated into their standard evaluation of chest pain in the ED/observation unit. Approximately half of the sites will be FFR_{CT} sites who will have CCTA and FFR_{CT} analysis incorporated into their standard evaluation of chest pain in the ER/observation unit. Sites who have CCTA but not FFR_{CT} incorporated into the ED/observation unit will be control sites.

If FFR_{CT} is implemented at a control site during the enrollment period, site can request to switch over to the non-control arm once FFR_{CT} has been successfully implemented. This switch must be reviewed and approved by the HeartFlow Clinical Research team.

No site may enroll more than 75 (15%) subjects in the trial.

IV. B. Patient Population

The population for this study will be clinically stable, symptomatic patients who present to the ED or observation unit with suspected CAD and while in the ED or observation unit, have a CCTA performed which shows at least one >40% lesion and no lesions >90% in a major epicardial vessel, a successfully processed FFR_{CT} (if applicable), and no history of coronary artery disease.

IV. C. General Inclusion and Exclusion Criteria

Inclusion Criteria (all must be present):

1. Age ≥18 years
2. Clinically stable, symptomatic patients who present to ED/observation unit with suspected CAD
3. CCTA shows at least one >40% lesion and no lesions >90% in at least one major epicardial vessel
4. FFR_{CT} processed successfully (if applicable)
5. EKG with no acute ischemic changes
6. Willing to comply with all aspects of the protocol, including adherence to follow up visit
7. Agrees to be included in the study
8. Able to provide written informed consent

Exclusion criteria (all must be absent):

1. CCTA showing no >40% lesion in a major epicardial vessel

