 - e. Decision plan prior to FFR_{CT} results (non-control sites)

V. D. Enrollment

All subjects must provide written informed consent prior to enrollment. A notation will be made in the subject's medical chart, if required by the institution, and in the study records that he/she is participating in the study, has had his/her questions answered, has read, signed, and dated the Informed Consent Form (ICF), and been given a copy of the ICF.

All subjects who meet eligibility requirements will be asked to participate. Subjects will be considered enrolled in the study after the following criteria have been met:

1. Informed consent form has been signed and subject has been provided a copy.
2. All inclusion criteria and no exclusion criteria have been met.

V. E. Follow up

A 30 day (± 7 days) follow up phone call with the subject following baseline visit will be done as a part of this study. Data collected will include:

- Current cardiac health status
- Any additional hospital admissions

- Any additional ED/observation unit visits
- Any cardiac procedures/tests
- MACE

Sites will also be asked to provide billing information (UB-04 preferred) from baseline to day 30. Reports and images for CCTA, FFR_{CT} (if applicable), ICA, and other cardiac tests will be uploaded to the eCRF.

VI. STUDY DURATION

The anticipated enrollment duration of ADVANCE-ED will be approximately 18 months. A 30 day follow up phone call is planned for this study.

VI.A. Rules for Subject Withdrawal

Each subject is free to withdraw from the study at any time. No additional data will be collected after a subject informs the Investigator that they want to withdraw.

VI. B. Rules for Terminating the Study

There are no formal termination criteria for this study. The sponsor reserves the right to terminate ADVANCE-ED at any time. Investigators have the responsibility to comply with all applicable regulatory guidelines and regulations. Specific reasons which may cause the sponsor, the Institutional Review Board, or local regulatory authorities to terminate a center include, but are not limited to:

- 1) Failure of the investigator to comply with investigator agreement, protocol, guidelines, and/or regulations.
- 2) Serious protocol violations.
- 3) Submission of knowingly false information from the research facility to the sponsor, clinical monitor, or other party involved in the study.

VI. C. Rules for switching from Control arm

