Sites who do not have FFR_{CT} incorporated into the ED/observation unit will be control sites. If FFR_{CT} is implemented at a control site during the enrollment period, site can request to switch over to the non-control arm once FFR_{CT} has been successfully implemented. This switch must be reviewed and approved by the HeartFlow Clinical Research team.

VI.D. SAFETY ASSESSMENT

Patients will undergo a clinically indicated CCTA and any other invasive physiological measurements, which do not require additional radiation, extra contrast, or additional procedure time for this study/protocol. All procedures performed will be per standard clinical care, and data obtained will be documented as per standard of clinical care. Therefore, there will be no additional clinical risks for subjects who participate. MACE will be collected at day 30. MACE is defined as the composite rate of all cause death, non-fatal myocardial infarction (MI) and unplanned hospitalization for acute coronary syndrome (ACS) leading to urgent revascularization.

VI.E. RATIONALE AND ETHICAL CONSIDERATIONS

This prospective, multi-center study is being conducted to provide real world evidence potentially in support of including FFR_{CT} in an ED pathway.

The potential risks to subjects participating in this study include potential breach of confidentiality. Data transmitted to HeartFlow will not contain any PHI identifiers and will be coded with a unique identifier for each subject. All applicable study data will be transferred to HeartFlow and core laboratories in a secure manner and in accordance with all applicable regulations.

Anticipated benefits

There are no specific benefits to subjects participating in the study. There may be some benefit to other patients who undergo FFR_{CT}-guided management in the future.

Anticipated risks

ADVANCE-ED is a prospective study which collects data from clinically-indicated CCTA imaging and other procedures. These procedures will have been planned as part of routine clinical practice; therefore, no additional clinical risks are related to participating in the study.

IX. STATISTICAL CONSIDERATIONS

IX. A. General Considerations

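### The day-30 MACE and catheterization rates rest on one call allowed from day 23 to day 37, and no rule aligns events to day 30

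*Combined protocol and SAP*

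**What the plan says.** Section III.B lists "Major Adverse Coronary Event (MACE) rates at day 30" and "Rate of invasive catheterization without obstructive disease at day 30" among the secondary endpoints. Section VI.D adds that "MACE will be collected at day 30" and includes death from any cause in the composite.

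The synopsis describes one contact: "There will be a 30-day follow-up phone visit following the baseline visit". Section V.E sets its window: "A 30 day (± 7 days) follow up phone call with the subject". The call gathers MACE, further admissions, ED visits, and cardiac procedures or tests.

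Two further sources appear in section V.E:

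- Billing, with a fixed end: "Sites will also be asked to provide billing information (UB-04 preferred) from baseline to day 30".
- Test reports and images, with no end date: those for "ICA, and other cardiac tests will be uploaded to the eCRF".

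The synopsis (Study Design and Methods) uses a different limit. It lists 30-day clinical outcomes and billing, and then other visits, imaging and "procedural data completed prior to the follow-up 30-day visit". That limit is the visit, not study day 30.

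The protocol does not require contact on or after day 30, a later check for subjects called early, or exclusion of events after day 30. It gives no method for unequal follow-up. Section IX.A leaves detailed methods to a SAP.

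**The concern.** The endpoint has a fixed horizon and the main means of observing it does not. A subject called on day 23 has completed follow-up under the protocol, yet that call cannot report a death or admission on day 27. A subject called on day 37 can report a day-35 event, and nothing says it must be set aside. Under the synopsis wording, a catheterization on day 26 after a day-23 call falls outside the visit and procedure data, although the billing period in section V.E would include it.

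The 30-day rates are at stake. They could be too low where calls are early and too high where calls are late. Section IX.D says the control arm contributes only to secondary endpoints, so these are the endpoints on which the arms can be set against each other. Arms are defined by site and are not randomized, and a difference in call timing between sites would pass into that comparison.

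**Working it through.** **The plan's own figure.** The only sample-size figure is n = 208 for an exact 95% interval of width 0.14 at a proportion of 0.5 (section IX.D). The Clopper-Pearson interval for 104/208 is 0.4301 to 0.5699, width 0.1399, and 208 is the smallest n with width at most 0.14. The figure reproduces. It concerns reclassification and does not depend on the call window.

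**The window.** Earliest call: 30 − 7 = day 23. Latest call: 30 + 7 = day 37. Largest part of the 30 days not covered by the call: 7/30 = 23.3%. Largest overrun: 7 days.

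**Average loss.** Assume calls spread evenly over days 23 to 37 and events capped at day 30. Half the calls are early and lose 3.5 days on average, so the mean loss is 0.5 × 3.5 = 1.75 days (5.8% of 30). Counting 15 whole days instead gives (7+6+5+4+3+2+1)/15 = 28/15 = 1.87 days (6.2%).

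Both figures need the day-30 cap, which the protocol does not contain. Without it, mean follow-up under even calls is (23 + 37)/2 = 30.0 days. Early losses and late gains then nearly cancel, and the net bias is about zero.

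**Events.** The protocol gives no event rate, so the 30-day rate p is assumed to be 1%, 2%, 5% or 10%. Further assumptions are a constant hazard, 250 subjects per arm (section IX.D) and no source other than the call. The probability of an event by day t is F(t) = 1 − (1 − p)^(t/30).

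- All calls on day 23: missed = 250 × [p − F(23)]. At p = 1%, F(23) = 0.00768 and 250 × 0.00232 = 0.6. At p = 10%, F(23) = 0.0776 and 250 × 0.0224 = 5.6.
- Even calls with a cap: missed = 250 × [p − mean of F(min(t, 30))].
- Extreme contrast, one arm all on day 23 and the other all on day 37 with no cap: F(37) − F(23).

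| Assumed 30-day rate | Expected events per 250 | Missed, all calls day 23 | Missed, even calls, capped at day 30 | Extreme arm difference (percentage points) |
|---|---|---|---|---|
| 1% | 2.5 | 0.6 | 0.15 | 0.5 |
| 2% | 5 | 1.2 | 0.29 | 0.9 |
| 5% | 12.5 | 2.9 | 0.71 | 2.3 |
| 10% | 25 | 5.6 | 1.4 | 4.4 |

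**Outer bounds as ratios.** With no true difference, day 23 against day 30 gives about 23/30 = 0.77, and day 23 against an uncapped day 37 gives about 23/37 = 0.62.

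**If events cluster early.** Follow-up starts at an acute presentation, so a constant hazard may overstate the loss. If a share s of the 30-day events falls by day 23, the all-day-23 loss is 250 × p × (1 − s). For s from 0.95 down to 0.90 this is 0.13 to 0.25 events at p = 1%, and 1.25 to 2.5 at p = 10%.

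**The case against.** The strongest reply is that section V.E does not rely on the call alone. Billing runs to day 30 whatever the call date, and angiography reports are uploaded without a cut-off. An admission, catheterization or urgent revascularization at the enrolling site on days 24 to 30 can therefore be found. This stands, and it rules out the tempting reading that the last 7 days are simply unobserved. What remains is narrower: deaths outside hospital and care elsewhere, to the extent that site billing does not show them. The protocol does not say whether it does, or whether billing feeds the MACE count. With no Clinical Events Committee (section XI.E), no committee is charged with reconciling the sources.

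A reader might also infer that the arms will differ in call timing, and take 0.77 or 0.62 as the likely distortion. The documents do not support that. The window is the same in both arms and nothing predicts a difference. The ratios need every subject in an arm of about 10 sites to be called on the same extreme day, with no help from billing. Likewise, no text says that a subject called on day 23 counts as event-free to day 30; the protocol is silent on the point.

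Finally, a SAP is promised, only secondary endpoints are involved, and section IX specifies no between-arm test of MACE. All of this is true and limits the weight of the point. A SAP can exclude events after day 30 if they are dated, but it cannot supply follow-up that was never collected.

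**Conclusion.** The point holds as a cheap improvement that affects secondary endpoints only. Following the protocol as written allows follow-up of unequal length behind rates that are defined at day 30. The synopsis and section V.E also give different limits for what is collected.

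The likely size is small: about 0.15 to 1.4 missed events per arm under even calls with a day-30 cap, and 0.6 to 5.6 in the all-day-23 case. Both ranges rest on assumed rates of 1% to 10%, a constant hazard and no other data source. Useful billing data or early clustering of events would shrink them. At the low rates only 2.5 to 5 events per arm are expected, so even one misassigned event would be visible. A difference between arms is possible because sites define the arms, but nothing in the documents predicts one, and the ratios above are bounds, not estimates. The primary reclassification endpoint is unaffected.

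**What to change.** 1. Set the call window to day 30 through day 37 (−0/+7). Alternatively, keep the present window and require a record and vital-status check through day 30 for anyone called earlier.
2. Record the date of every event in the eCRF, and count in the day-30 endpoints only events dated on or before day 30, in both arms.
3. State which sources ascertain MACE and catheterization, and whether they include care at other hospitals.
4. Reconcile the synopsis cut-off (the follow-up visit) with the billing period in section V.E (day 30).

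The cost is a minor protocol amendment with IRB approval (section XI.A) and an eCRF date check. The narrower window leaves 8 allowable days instead of 15, which may cause a few more missed calls. The record-check alternative avoids that at the price of extra site work. The sample size does not change.

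### The withdrawal rule stops all data collection and offers no contact-only option, so 30-day record-based outcomes are lost needlessly for some subjects

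*Combined protocol and SAP*

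**What the plan says.** Section VI.A is two sentences long. The first sets the trigger: "Each subject is free to withdraw from the study at any time". The second sets the consequence: "No additional data will be collected after a subject informs the Investigator that they want to withdraw". It gives no degrees of withdrawal. It implies that data already entered are kept but does not say so, and it does not mention routine-care records that exist at withdrawal but have not yet been abstracted.

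The other relevant text concerns where the data come from:

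- Section IV, on clinical data: "All non-invasive and invasive data collected will be obtained from clinical practices that are standard clinical care".
- Section IV, on management data: "All details about cardiovascular testing and treatment (planned and actual) will be recorded at baseline".
- Section V.E, on the subject's part in follow-up: a 30-day "follow up phone call with the subject following baseline visit will be done as a part of this study". Cardiac status, admissions, visits, procedures and MACE are listed as data from it.
- Section V.E, on costs: "Sites will also be asked to provide billing information (UB-04 preferred) from baseline to day 30". Test reports and images are uploaded as well.
- The Synopsis (Study Design and Methods) has sites supply length of stay, bills, 30-day outcomes, and visit, imaging and procedure data up to the follow-up visit. It does not make these depend on the call.
- Section VI.D: "MACE is defined as the composite rate of all cause death, non-fatal myocardial infarction (MI) and unplanned hospitalization", the hospitalization component being for acute coronary syndrome with urgent revascularization.

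Section IX.B plans to report reasons for discontinuation. The documents give no expected withdrawal rate and no missing-data method; Section IX.A defers methods to a SAP.

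**The concern.** After enrolment, the only study contact described is one phone call. The rest of the 30-day picture (bills, angiography reports, procedures, readmissions to the same hospital) exists in the site's records whether or not the subject speaks to the study. A rule that closes those records whenever a subject withdraws discards data that some subjects would have been content to leave open.

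The exposed endpoints are 30-day MACE, catheterization without obstructive disease, and cost. The control arm contributes only to secondary endpoints, so these are what its roughly 250 subjects are enrolled for. Withdrawal may be related to outcome or to satisfaction with care. It may also differ between control and FFRCT sites, which are different hospitals with no blinding. Data that were never collected cannot be recovered later by an analysis plan.

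A related gap is in V.E. MACE, which includes all-cause death, is listed under a call with the subject, and no step is given for when that call fails.

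**Working it through.** **1. The plan's own figure.** Section IX.D states that 208 subjects give a two-sided 95% exact interval of width 0.14 at a reclassification proportion of 0.5. The Clopper-Pearson interval at n = 208, x = 104 runs from 0.4301 to 0.5699, a width of 0.1399. At n = 207 the width is 0.1402. So 208 is the smallest n that meets the target, and the figure reproduces.

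**2. Room for loss in the primary endpoint.** About 250 are to be enrolled in the FFRCT arm. 250 − 208 = 42, and 42/250 = 16.8%. With all 250 usable the width is 0.127. The stated precision fails only if primary-endpoint data are lost for more than 16.8% of the arm.

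**3. Effect on 30-day MACE, by assumption.** The documents give no inputs, so the withdrawal share w and the observed MACE rate are both assumed. Take one arm of 250, with m subjects withdrawn whose day-30 status is unknown and x events seen in the other 250 − m. The full-arm rate then lies between x/250 (no events among the withdrawn) and (x + m)/250 (all had events). The range has width m/250, whatever x is.

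| w | m | x | Possible full-arm rate | Range width | Exact 95% CI width, x of 250 − m |
|---|---|---|---|---|---|
| 2% | 5 | 2 | 0.8% to 2.8% | 2.0 points | 2.8 points |
| 2% | 5 | 5 | 2.0% to 4.0% | 2.0 points | 4.0 points |
| 5% | 12 | 2 | 0.8% to 5.6% | 4.8 points | 2.9 points |
| 5% | 12 | 7 | 2.8% to 7.6% | 4.8 points | 4.8 points |
| 10% | 25 | 2 | 0.8% to 10.8% | 10.0 points | 3.1 points |
| 10% | 25 | 7 | 2.8% to 12.8% | 10.0 points | 5.0 points |

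At 2% withdrawal, sampling error is the larger uncertainty. At about 5% the two are of similar size or the missing data dominate, and at 10% the missing data clearly dominate. The upper bounds assume that every withdrawn subject had an event, so they are limits and not forecasts.

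**4. How much the fix could recover.** If a share g of withdrawing subjects would accept record review, and the records settle their status, the range shrinks from m/250 to (1 − g)m/250. The documents give no basis for g. The widths in the table are therefore the most that could be avoided, not the expected gain.

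**The case against.** Stopping collection when consent is truly withdrawn is legitimate and open to IRB review; it is not an error. That stands. The criticism is only that the subject is given no lesser choice.

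The consent pages are not among the documents, and a contact-only option may be there. That also stands. If so, VI.A as written contradicts it and still needs aligning.

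Withdrawals may be few. There is one call at 30 days, and the eligibility criteria exclude people unwilling or unable to complete follow-up. This is a fair reason to expect the low end of the assumed range.

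A reader might infer three stronger points that the documents do not support:

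- *That declining or missing the call triggers the rule.* It does not. The trigger is telling the investigator of a wish to leave the study. The text does leave room for a site to treat a refused call as a withdrawal, because it does not separate the two.
- *That an unanswered call loses bills, test reports and outcomes in the same way.* The Synopsis and V.E have sites supply these without making them conditional on the call. What is missing is an explicit step for establishing death or MACE when the call fails, which is a separate gap from VI.A.
- *That the primary endpoint is at risk.* Planned and delivered management are recorded at baseline, and the arm can lose 42 subjects before the stated precision is missed.

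Nor are all the data from routine records: the plan made before FFRCT is asked of the treating provider (Section I), and V.E lists current cardiac health status under the call.

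**Conclusion.** The point holds in limited form. VI.A is all-or-nothing in a study whose outcome data mostly lie in routine-care records and site bills. It therefore loses later MACE, deaths, catheterization findings and bills for withdrawing subjects who would have allowed record review. Read literally, it also bars bills for a completed index stay that have not yet been collected at withdrawal.

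The loss falls on secondary endpoints. Its size is unknown. The 2 to 10 point widening of the possible 30-day MACE rate rests on an assumed 2% to 10% withdrawal in an arm of 250 with day-30 status unknown for all of them, and only part of it is avoidable. The figures do not show that MACE will be biased, or in which direction. The change is worth making because it is cheap and the lost data cannot be recovered afterwards.

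**What to change.** Replace the second sentence of VI.A with:

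> A subject may withdraw from further contact only, or from all further data collection; the choice and its date are recorded. Unless the subject chooses the second, the site continues to collect medical-record, billing and vital-status data to day 30. Data collected before full withdrawal are kept; records from before that date not yet abstracted are used only if the consent form permits it.

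Align the consent form with this text, and report the number in each category by arm.

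Separately, add to V.E:

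> If the call cannot be completed, the site checks available records and vital status to day 30 before recording the outcome as missing.

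The cost is protocol and consent wording with IRB review, one eCRF field for type of withdrawal, and a little chart review for a few subjects. No visits, tests or subjects are added. One limit remains: a site's own records may not show events treated elsewhere, so some outcomes will still be missing.
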